1. GLOSSARY OF ABBREVIATIONS AND DEFINITIONS

1.1. Glossary of Abbreviations

Abbreviation	Description
AE	Adverse Event
ADR	Adverse Drug Reaction
ATC	Anatomical Therapeutic Chemical
ANOVA	Analysis of Variance
AAV9	Adeno-associated virus serotype 9
ALT	Alanine Aminotransferase
AST	Aspartate Aminotransferase
BDRM	Blinded Data Review Meeting
BLQ	Below Levels of Quantification
BMI	Body Mass Index
CI	Confidence Interval
CK-MB	Creatine kinase isoenzyme
CMAP	Compound Motor Action Potential
CRF/eCRF	Case Report Form/ electronic Case Report Form
CTCAE	Common Terminology Criteria for Adverse Events
CSR	Clinical Study Report
CV	Coefficient of Variation
DMC	Data Monitoring Committee
DSMB	Data Safety Monitoring Board
ECG/EKG	Electrocardiogram/Electrocardiogram
ELISAs	Enzyme-Linked Immunosorbent Assays
ELISpot	Enzyme-Linked ImmunoSpot
FDA	U.S. Food and Drug Administration
GCP	Good Clinical Practice

Abbreviation	Description
GPP	Good Pharmacoepidemiology Practice
HEENT	Head, eyes, ears, nose, throat
HLT	High Level Term
ICH	International Conference on Harmonization
ITT	Intent-To-Treat
IVRS	Interactive Voice Response System
IWRS	Interactive Web Response System
MAR	Missing at random
Max	Maximum
MCAR	Missing completely at random
MedDRA	Medical Dictionary for Regulatory Activities
Min	Minimum
N/A	Not Applicable
NA	Not Applicable
NCI	National Cancer Institute
NTF	Note-To-File
OR	Observational Research
PASS	Post Authorization Safety Study
PAES	Post Authorization Efficacy Study
PBMC	Peripheral Blood Mononuclear Cells
PCS	Potentially Clinically Significant
PD	Pharmacodynamic
PDS	Pharmacodynamic Set
PK	Pharmacokinetic
PKS	Pharmacokinetic Set
PNCR	Pediatric Neuromuscular Clinical Research Network

Abbreviation	Description
PT	Preferred Term
QC	Quality Control
QTc	Corrected QT Interval
SAE	Serious Adverse Event
SAP	Statistical Analysis Plan
SD	Standard Deviation
SDTM	Study Data Tabulation Model
SE	Standard Error
SFC	Spot forming cells
SI	Standard International System of Units
SMN	Survival Motor Neuron
SMQ	Standardized MedDRA Queries
SOC	System Organ Class
SOP	Standard Operating Procedure
SS	Safety Set
TEAE	Treatment Emergent Adverse Event
TLF	Table, Listing and Figure
WHO	World Health Organization

1.2. Glossary of Definitions

Abbreviations list pertains to the SAP only.

Abbreviation	Description
AE	Adverse Event: Any untoward medical occurrence in a clinical investigation subject which does not necessarily have a causal relationship with the drug or device under study.
Age	For a given event, age will be expressed in days or months and rounded to one decimal place for months. A month is standardized to a period of 30 days.

Abbreviation	Description
	Age at Event = (Date of Event – Date of Birth + 1)/ 30 (displayed as months). Age at Baseline = (Date of Gene Therapy Infusion – Date of Birth + 1)/ 30 (displayed as months).
Baseline	Baseline, e.g., in terms of baseline laboratory values, vital signs, or physical exam results, refers to a measurement or evaluation made prior to initiation of gene therapy infusion. If there are multiple measurements prior to the initiation of gene therapy infusion, only the latest measurement in most cases will be considered as baseline for analysis purposes or defined specifically.
BiPAP	Bilevel Positive Airway Pressure, a form of non-invasive mechanical pressure support ventilation.
CHOP-INTEND	Children's Hospital of Philadelphia Infant Test of Neuromuscular Disorders, a 16-item motor function assessment validated for use in infants with spinal muscular atrophy.
CMAP	Compound Muscle Action Potential, the total electrophysiological output in a muscle or muscle group recorded by surface electrodes following supramaximal stimulation of the innervating nerve.
Day 1	The day of the gene therapy treatment
Dose	Total vector genome delivered (in vg /patient weight on Day – 1(kg)).
MedDRA	Medical Dictionary for Regulatory Activities is a medical terminology used to classify adverse event information associated with the use of biopharmaceuticals and other medical products.
CTCAE	Common Terminology Criteria for Adverse Events version 4.03. The CTCAE is descriptive terminology, involving a severity scale, which is used for AE reporting in particular for unique patient populations. It is a subset of MedDRA terminology.
Permanent Ventilation	Requirement of \geq 16-hour respiratory assistance per day (includes BiPAP) continuously for \geq 14 days in the absence of an acute reversible illness, excluding perioperative ventilation.
PNCR	Pediatric Neuromuscular Clinical Research Network
Study Day	For any event of interest, Study Day = calendar date of event – calendar date of gene transfer +1. Day 1 is the Study Day of the gene transfer and any events occurring on the same calendar day as the gene transfer.
TEAE	Treatment-emergent Adverse Event = any adverse event whose onset (or worsening of an existing AE) occurred on or post day of gene therapy infusion.

Abbreviation	Description
Vector genome	The human SMN cDNA sequence, corresponding to the mature mRNA, cloned into the self-complementary AAV vector plasmid.

2. PURPOSE

The purpose of this document is to provide further details about the statistical analysis methods, data derivations and data summaries to be employed in the study protocol 15699-AVXS-101-CL-303: *Phase 3, Open-Label, Single-Arm, Single-Dose Gene Replacement Therapy Clinical Trial for Patients with Spinal Muscular Atrophy Type 1 with One or Two SMN2 Copies Delivering AVXS-101 by Intravenous Infusion*. This statistical analysis plan (SAP) has been based on International Conference on Harmonization (ICH) E3 and E9 guidelines and in reference to protocol version 1.0: dated 29 March 2017 and Annotated Case Report Form (aCRF): dated 17 August 2017. The statistical analysis plan covers statistical analysis, tabulations and listings of all data including effectiveness and safety data. Analyses will be performed using SAS® Version 9.4 (SAS Institute, Inc., Cary, NC) or later under the Windows (Server 2008 R2) operating system.

This SAP supersedes the statistical considerations identified in the protocol; where considerations are substantially different, they will be so identified.

2.1. Responsibilities

AveXis, Inc. is responsible for ownership and approval of the SAP.

██████████ is responsible for deriving the data set according to CDISC standards and create data set specifications based on the SAP. ██████████ will perform the statistical analyses and are responsible for the production and quality control of all tables, listings and figures.

2.2. Timing of Analysis

The primary analysis will occur at such time that the last intent-to-treat (ITT) patient has reached 18 months of age; database lock will occur after all enrolled patients have completed the 18 months of age visit or have discontinued study early.

2.2.1. DSMB Quarterly Data Reviews

The DSMB's primary responsibilities will be to:

- safeguard the interests of study patients and assess the safety of the study treatment(s) and study procedures in a confidential manner
- assess the data quality, completeness and timeliness and provide recommendations about stopping or continuing the studies or otherwise modifying the studies
- contribute to enhancing the integrity of the studies, by formulating recommendations relating to the patient recruitment, selection and patient management during the studies
- further enhance the ability to evaluate the cumulative safety data by making recommendations regarding the format of the statistical summaries in the open and closed reports
- attend to safety and risk: benefit considerations in tandem with study designs, planned objectives, and patient care in accordance with ICH, FDA, EMA, Declaration of

Helsinki, and Operational Guidelines for Establishment and Function of Data Safety Monitoring Boards/Data Monitoring Committees

- consider factors external to the studies when relevant information becomes available, such as scientific or therapeutic developments that may have an impact on the safety of the participants or the ethics of the studies
- review the conduct of the studies including protocol violations

The DSMB will serve in an advisory role to the AveXis Study Team. AveXis representatives will be responsible for promptly reviewing the DSMB recommendations, determining whether any changes to the studies are required (including protocol amendments), and initiating any changes to the studies.

2.2.2. DSMB Reporting and Meetings

Reports describing the status of the study will be prepared by AveXis and sent to each DSMB member prior to each meeting for review and preparation. DSMB meetings will occur on quarterly basis, aligning with the AveXis quarterly data cut reviews (as AVXS summary report completed in following month).

Reports include the following:

- A brief narrative of the study status, including the target enrollment, current and projected time to completing enrollment. Any significant events and/or difficulties should be briefly described in this narrative.
- A brief narrative for each participant describing gender, age, race and ethnicity and other relevant demographic characteristics. The narrative for each participant should briefly describe his/her study status (i.e., dose level, visit number, adverse event information).
- A timeline outlining the study progress relative to visit number for each participant, as well as time points for each SAE/Dose Limiting Toxicity. A total for Adverse Events (AEs) for each participant should be included.
- A summary of AEs by grade levels
- A listing of AE details grouped by participant
- A listing of SAE details grouped by participant
- A listing of deaths
- A summary of clinically significant laboratory test results
- Other key information related to safety/conduct of the study

2.2.3. Stopping/Discontinuation Rules

An independent Data Safety Monitoring Board (DSMB) has been selected for the study. Safety data will be monitored on a continual basis throughout the trial in accordance with ICH/GCP and institutional requirements, including Sponsor Safety Management Plan (SMP). The DSMB could recommend early termination of the trial for reasons of safety. Study enrollment could be halted by the Sponsor when any patient experienced a Grade 3 or higher adverse event toxicity that is possibly, probably, or definitely related to the study drug. This

includes any patient death, important clinical laboratory finding, or any severe local complication in the injected area related to administration of the study agent.

The DSMB charter and all materials developed for the DSMB to review and all documented recommendations will be maintained according to confidentiality requirements.

3. STUDY OBJECTIVES

[figure not shown]
3.1. Primary Objective(s)

The co-primary objectives of this gene therapy clinical trial are to determine the efficacy of AVXS-101 by demonstrating achievement of developmental milestone of functional independent sitting for at least 30 seconds at the 18 months of age study visit and to determine the efficacy of AVXS-101 based on survival at 14 months of age. Survival is defined by the avoidance of combined endpoint of either (a) death or (b) permanent ventilation, which is defined by tracheostomy or by the requirement of ≥ 16 hours of respiratory assistance per day (via noninvasive ventilatory support) for ≥ 14 consecutive days in the absence of an acute reversible illness, excluding perioperative ventilation. Permanent ventilation, so defined, is considered a surrogate for death.

3.4. Safety Objectives

The safety objectives are to:

- Evaluate the safety of AVXS-101 in patients with SMA Type 1
- Determine the safety of AVXS-101 based on the development of unacceptable toxicity defined as the occurrence of any Common Terminology Criteria for Adverse Events (CTCAE) [CTCAE 04] Grade 3 or higher, unanticipated, treatment-related toxicity.

3.5. Study Design

[figure not shown]
This is a pivotal Phase 3, open-label, single-arm, single-dose, study assessing the efficacy and safety of AVXS-101 (gene replacement therapy) in up to twenty (20) patients with spinal muscular atrophy (SMA) Type 1 who meet enrollment criteria, may be either symptomatic or pre-symptomatic and are genetically defined by no functional survival motor neuron 1 gene (*SMN1*) with 1 or 2 copies of survival motor neuron 2 gene (*SMN2*) and who are < 6 months (< 180 days) of age **at the time** of gene replacement therapy (Day 1). Enrolling up to twenty (20) patients under the broader enrollment criteria is projected to enable enrollment of at least fifteen (15) patients that meet the Intent-to-Treat Population (ITT) criteria. The ITT

population is identified as symptomatic patients with bi-allelic *SMN1* deletions and 2 copies of *SMN2* without the *SMN2* gene modifier mutation (c.859G>C) and will comprise the primary population for evaluation of the primary and secondary endpoints. Study power is based upon efficacy analysis of the ITT population. Furthermore, the first three patients enrolled must meet criteria for the Intent-To-Treat Population to enable a comparison of CHOP-INTEND scores at one-month following gene replacement therapy to enable a comparison of patient response between AVXS-101-CL-303 patients and Cohort 2 patient results from the Phase 1 trial (AVXS-101-CL-101). Patients with 1 copy of *SMN2*, pre-symptomatic patients and patients with the *SMN2* gene modifier mutation (c.859G>C) and other permutations outside of those specified in the ITT population will be evaluated separately as part of additional subgroup analyses. Details of all analyses will be contained within this Statistical Analysis Plan.

This is a Phase 3, open-label, single-arm, single-dose study of AVXS101 (gene replacement therapy) in patients with SMA Type 1 with 1 or 2 copies of *SMN2*. The study includes 3 study periods: screening, gene replacement therapy, and follow-up (Figure 1). During the screening period (Days -30 to -2), patients undergo screening procedures to determine eligibility for study enrollment. Those who meet the entry criteria will enter the in-patient gene replacement therapy period (Day -1 to Day 3). On Day -1, patients will be admitted to the hospital for pre-treatment baseline procedures. On Day 1, patients will receive a one-time IV infusion of the equivalent of AVXS-101 1.1×10^{14} vg/kg over approximately 30–60 minutes, dependent upon total volume required per patient weight, and will undergo in-patient safety monitoring over the next 48 hours. Patients may be discharged 48 hours after gene replacement therapy, based on investigator judgment. During the outpatient follow-up period (Day 4 to End of Study at 18 months of age), patients will return at regularly scheduled intervals for efficacy and safety assessments until the patient reaches 18 months of age. Any missed visit should be rescheduled as soon as possible, but within 7 days and still within the required visit window.

All post-treatment visits will be relative to the date on which gene replacement therapy is administered, except for the 14 and 18 months of age visits, which will be relative to the patient's date of birth. For the 14 and 18 months of age visits, the patient will return within 0 to 14 days after the date on which the patient reaches 14 and 18 months of age, respectively. The 18 months of age visit will also serve as the End of Study visit. After the End of Study visit, eligible patients may roll over into the long-term follow-up study.

Figure 1: Study Design Schematic

Note: After the End of Study visit at 18 months of age, eligible patients may directly roll over into the long-term follow-up study.

ET = early termination

a All post-treatment visits will be relative to the date on which gene replacement therapy is administered, except for the 14 and 18 months of age visits, which will be relative to the patient's date of birth.

A schedule of study assessments is provided in [Table 1](#). Efficacy will be assessed by primary, secondary, [REDACTED] endpoints (see [Section 4.1, Efficacy Endpoints](#): (see [Section 8 for Details](#)) and [REDACTED]

[REDACTED]. Safety will be assessed through monitoring AEs, concomitant medication usage, physical examinations, vital sign assessments, cardiac assessments, and laboratory evaluations (see [Section 4.3, Safety Endpoint](#) through [Section 4.8, Other Endpoints](#)).

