3.5.1. Schedule of Assessments

Table 1: Schedule of Assessments

Study Period	Screening	Gene Replacement Therapy (In-patient)				Follow-up (Outpatient)					End of Study ^a
		1	2			3	4	5	6	7+	
Visit #		-1	1 ^b	2	3	7	14	21	30	Monthly ^c	18 Months of Age (or ET)
# of Days in Study	-30 to -2	-1	1 ^b	2	3	7	14	21	30	Monthly ^c	18 Months of Age (or ET)
Window						± 2 days					± 7 days (0–14 days at 14 Months of Age)
Informed Consent	X										
Prednisolone Pre-Dosing		X ^q	X	X	X	X	X	X	X ^q		
AVXS-101 Infusion			X								
Bayley Scales/WHO Developmental Milestones ^d (with video) ^e	X								X ^f	X ^f	X
CHOP-INTEND ^g (with video) ^e	X	X ^s				X	X	X	X	X	X
CMAP	X									X ^j	X
Demographic/Medical History	X										
Physical Exam	X		X	X	X	X	X	X	X	X	X
Vital Signs ^h /Weight & Length	X	X	X ⁱ	X	X	X	X	X	X	X	X
12-Lead ECG	X	X	X	X						X ^{j,t}	X
12-Lead Holter Monitoring ^k		X	X	X	X					X ^{j,t}	X
Echocardiogram	X									X ^{j,t}	X
Pulmonary Examination	X	X		X	X	X	X	X	X	X	X
Swallowing Test	X									X ^j	X
Photograph of Infusion Site			X	X	X	X	X	X	X		

Study Period	Screening	Gene Replacement Therapy (In-patient)				Follow-up (Outpatient)					
		1	2			3	4	5	6	7+	End of Study ^a
Visit #	1		2			3	4	5	6	7+	End of Study ^a
# of Days in Study	-30 to -2	-1	1 ^b	2	3	7	14	21	30	Monthly ^c	18 Months of Age (or ET)
Window						± 2 days			± 7 days (0–14 days at 14 Months of Age)	0–14 days	
Hematology/Chemistry/ Urinalysis	X	X ^o		X		X	X	X	X	X	X
CK-MB	X					X			X	X ^r	X
Virus Serology	X										
Capillary Blood Gas		X		X							
ELISA anti-AAV9/SMN Ab	X					X	X	X	X ^l		
Immunology Testing (ELISpot)						X			X ^l		
AAV9 Ab Screen in Mother	X										
Blood for Diagnostic Confirmation Testing	X										
Saliva, Urine, and Stool Samples (for viral shedding) ^p	X			X ^m	X ^m	X	X	X			
Adverse Events ⁿ	X	X	X	X	X	X	X	X	X	X	X
Prior and Concomitant Medications	Collected from 2 weeks before gene replacement therapy until End of Study visit										

Note: Missed visits should be rescheduled as soon as possible, but within 7 days.

Ab = antibody; CHOP-INTEND = Children's Hospital of Philadelphia Infant Test of Neuromuscular Disorders; CMAP = compound motor action potential; ECG = electrocardiogram; ELISA = enzyme-linked immunosorbent assay; ELISpot = Enzyme-linked ImmunoSpot; ET = early termination; WHO = World Health Organization

a The End of Study visit must occur within 0 to 14 days after the date on which the patient reaches 18 months of age (or ET).

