- s If a Day -1 CHOP-INTEND assessment is not completed, a CHOP-INTEND assessment should be completed on Day 1 prior to dose administration.
- t for patients enrolled in the study prior to amendment 3 and irrespective of study schedule, after signing an updated informed consent form, an echocardiogram, 24-hour Holter monitoring, and 12-lead ECG will be performed at the next scheduled visit and then in accordance with the Schedule of assessments Compound Motor Action Potential Manual

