4.2.1. CHOP-INTEND Score

There are 16 items in CHOP-INTEND assessment (Section 21.2). A rating of Brazelton behavioral states (Section 21.3) was recorded for each item. As suggested by manual [9], the optimal state for testing is state 4 (“alert, with bright look”) and 5 (“eyes open”). If a subject cannot be tested for an item due to an adverse behavioral state, it should be scored as “CNT” (cannot test) and NOT a zero. In item 1 to 11, 13 and 16, both left and right sides need to be evaluated, and the maximum score should be selected for the best score of the item. If both sides are scored “CNT”, the item should be scored as “CNT”. If only one side scored “CNT”, the other side score should be used for the best score of the item. If any of these 16 items scored “Cannot test” or “CNT”, the total score should be set missing.

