6.4. Visit Windows

For efficacy analysis, the time windows specified in

Table 4 describe how efficacy data will be assigned to protocol-specified time points, as displayed in the Schedule of Assessments in SAP [Section 3.5.1](#). All time points and corresponding time windows are defined based on Dosing Date.

If more than one efficacy observation for a specific assessment is included in a time window, the assessment closer to the nominal time will be used. If there are two efficacy observations equally distant to the nominal time, the latest one will be used in analyses. Any efficacy assessments occurring outside the analysis windows will be considered an assessment of an unscheduled visit.

Table 4: Analysis Time Windows of Bayley Scales, CHOP-INTEND, Development Milestones and Pulmonary Exam*

Scheduled Visit	Nominal Days (Study Day)	Acceptable Analysis Window in Study Days (Min Day – Max Day)
Baseline	-	<1
Month 1	30	1 to 44
Month 2	60	45 to 74
Month 3	90	75 to 104
Month 4	120	105 to 134
Month 5	150	135 to 164
Month 6	180	165 to 194
Month 7	210	195 to 224
Month 8	240	225 to 254
Month 9	270	255 to 284
Month 10	300	285 to 314
Month 11	330	315 to 344
Month 12	360	345 to 374
Month 13	390	376 to 404

Scheduled Visit	Nominal Days (Study Day)	Acceptable Analysis Window in Study Days (Min Day – Max Day)
Month 14	420	405 to 434
Month 15	450	435 to 464
Month 16	480	465 to 494
Month 17	510	495 to 539
Month 18	540	540 to 570
Final Treatment Visit and 14 Months of Age Analysis Window		0 to ≤14 days after patient reaches 14 months of age (420-434 days of age) visit window; 0 to ≤14 days after patient reaches 18 months of age (540 days of age) visit window

*Depending on age at time of dosing, patients will complete varying number of visits. The patient must complete a visit within 2 weeks after reaching 14 months of age; subsequent visits will be scheduled from that visit date. The patient must also complete the final study visit within 2 weeks after reaching 18 months of age.

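### Minor, but wrong as written: SAP Table 4 puts Study Day 375 in no window, puts a pre-dose Day 1 score in a post-dose window, and lets an earlier CHOP-INTEND score stand in for Month 1

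*SAP*

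**What the plan says.** - **Schedule (SAP 3.5.1, Table 1).** CHOP-INTEND is done at Screening, Day -1, Days 7, 14, 21 and 30, then monthly and at End of Study. Footnote s adds that if the Day -1 test is not done, "a CHOP-INTEND assessment should be completed on Day 1 prior to dose administration". Bayley has no assessment between Screening and Day 30. The pulmonary examination, like CHOP-INTEND, is done on Days 7, 14 and 21.
- **Analysis windows (SAP 6.4, Table 4).** One table serves Bayley, CHOP-INTEND, milestones and pulmonary exam, in study days from dosing. Baseline is before Day 1, Month 1 is 1 to 44 (nominal Day 30), Month 12 is 345 to 374 and Month 13 is 376 to 404. There are no weekly rows.
- **Selection (SAP 6.4).** When a window holds several observations, "the assessment closer to the nominal time will be used", and a tie goes to the later one. "Any efficacy assessments occurring outside the analysis windows will be considered an assessment of an unscheduled visit".
- **Baseline (SAP 6.2.1).** Baseline is the last non-missing value before infusion, and this includes pre-infusion values on Day 1.
- **CHOP-INTEND total (SAP 4.2.1).** If any of the 16 items cannot be tested (CNT), "the total score should be set missing".
- **Anchoring (SAP 3.5 and the Table 4 footnote).** Visits count from dosing, "except for the 14 and 18 months of age visits, which will be relative to the" date of birth. Visits after the 14-month visit are then scheduled from that visit.
- **Use of the one-month score (SAP 3.5, 3.6 and 3.7).** The first three patients must meet ITT criteria to "enable a comparison of CHOP-INTEND scores at one-month following gene replacement therapy" with Phase 1 Cohort 2.

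**The concern.** Table 4 decides which score carries which visit label. Three of its entries give a wrong or ambiguous label if programmed literally.

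- **(a) Day 375** has no study-day row, so an assessment on that day becomes unscheduled and leaves the by-visit summaries.
- **(b) A pre-dose Day 1 score** is baseline under section 6.2.1 but lies in Month 1 under Table 4. A programmer who follows Table 4 would fall back on the Screening score (Days -30 to -2) as baseline and file the true baseline as post-dose.
- **(c) The Month 1 window** has no lower limit above the infusion day, so it holds four scheduled CHOP-INTEND scores at different times since dosing. If the Day 30 total is lacking, an earlier score can be reported as Month 1.

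The one-month score is the one that section 3.5 names for the link to Phase 1. With three patients, one substituted score is a third of the data.

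**Working it through.** **Pattern of Table 4.** Most windows follow nominal day minus 15 to nominal day plus 14, for example Month 2 = 60 - 15 to 60 + 14 = 45 to 74. Of the 18 windows, 14 fit. The exceptions are Month 1 (1 to 44 against 15 to 44), Month 13 (376 to 404 against 375 to 404), and Months 17 and 18, which meet at Day 540. Checking every study day from 1 to 570 shows that only Day 375 is uncovered and that none is covered twice.

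**(a) Who can reach Day 375.**
- Dosing-anchored visits within ±7 days cannot. Month 12 spans 353 to 367, or at most 374 with 7 further days, and Month 13 starts at 383.
- For visits tied to age, age = age at dosing (a) + study day - 1. The 14-month visit, at 420 to 434 days of age, falls on study days 421 - a to 435 - a.
- Visits re-anchored to the 14-month visit, at 30-day spacing ±7 (assumption), can land on Day 375. For the first, 444 - a ≤ 375 ≤ 472 - a gives a = 69 to 97. The second gives 99 to 127 and the third 129 to 157.
- Assume dosing age uniform over 1 to 179 days and visit days uniform within their windows. Each of the three visits then hits Day 375 with probability 1/179, so 3/179 = 1.7% per infant. Over 20 infants that is 20 × 3/179 = 0.34 expected visits, and the chance of at least one is 1 - (1 - 3/179)^20 = 29%.

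**(b) Day 1.** Section 6.2.1 makes a pre-infusion Day 1 value baseline. Table 4 requires Baseline to be before Day 1 and opens Month 1 on Day 1. Both rules cannot hold for a child tested under footnote s. As a Month 1 candidate the Day 1 score is 30 - 1 = 29 days from nominal, so it loses to any total from Days 2 to 44. The practical risk is therefore mainly a wrong baseline.

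**(c) Month 1 selection.** Distances from Day 30 are 23 (Day 7), 16 (Day 14), 9 (Day 21) and 0 (Day 30).
- The extracted Table 1 does not show whether Day 30 carries ±2 or ±7 days, so both were tried, with the weekly visits at ±2. In all 625 combinations (±2) and all 1,850 (±7), the Day 30 score is chosen.
- If Day 30 is missed or has no total, the nearest remaining score is Day 21.
- If Day 30 is late, the latest in-window Day 21 visit (Day 23) is 7 days from nominal. A score on Day 37 ties and wins as the later one. A score on Day 38 is 8 days away and loses. Against a test on exactly Day 21, the Day 30 score loses from Day 40.

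**Size of a substitution.** Understatement = gain × (30 - day)/30, with gain the assumed linear rise over the first 30 days. The SAP gives no such figure.

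| Assumed gain in 30 days | Day 21 used for Month 1 | Shift in a three-patient mean |
|---|---|---|
| 5 | 5 × 9/30 = 1.5 | 0.5 |
| 10 | 10 × 9/30 = 3.0 | 1.0 |
| 15 | 15 × 9/30 = 4.5 | 1.5 |

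**The case against.** The strongest defence is that the plan already protects what matters.

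- **Selection rule.** Nearest-to-nominal keeps every on-schedule Day 30 score, and SAP 3.5 says "Any missed visit should be rescheduled as soon as possible, but within 7 days and still within the required visit window". This stands. A reader might infer that week-one scores routinely pose as one-month scores, but a Day 7 substitution needs the Day 14, 21 and 30 totals all to be absent. A Day 30 visit on Day 38 or later is outside its visit window on either reading of Table 1, although Table 4 still accepts it up to Day 44.
- **Weekly scores.** A reader might infer that the weekly scores are discarded. The documents do not show this. Section 8.3 is redacted, and the summary of changes shows that it contained further analyses, including statistical modeling.
- **Landmarks.** A reader might count 14- and 18-month visits among those lost on Day 375. They can fall there (dosing at 46 to 60 and 166 to 179 days of age), but the last row of Table 4 and section 6.2.3 select them by age, and section 6.4 allows further mapping. They should not be counted.
- **One-month comparison.** No visible hypothesis, test or endpoint uses it, and the readable text does not say that it draws on Table 4 rather than on the Day 30 visit itself. This stands and limits the weight of (c).
- **Day 1.** Section 6.2.1 gives the sensible answer. It does not remove the conflict, because Table 4 says otherwise and neither is stated to prevail.
- **Day 375.** Probably a one-digit slip, and the data are relabelled rather than deleted. Both are true, but a program will apply the stated limit.

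**Conclusion.** The three defects in Table 4 are real and minor. Day 375 is in no study-day row; under the uniform assumptions above, about 0.34 re-anchored visits in the whole trial would be relabelled unscheduled. The Day 1 entry contradicts section 6.2.1 for any child tested under footnote s. The Month 1 window permits an earlier score, normally Day 21, to be labelled Month 1 when the Day 30 total is missing or late. That understates the one-month gain by 3.0 points (1.5 to 4.5) per substituted child, or 1.0 point (0.5 to 1.5) in a three-patient mean, if the assumed linear gain of 10 points (5 to 15) holds and the comparison uses Table 4 windows. Co-primary and co-secondary landmark results are not affected, because section 6.2.3 selects them by age. Whether weekly scores are summarized elsewhere cannot be judged from the readable text.

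**What to change.** In section 6.4, Table 4:

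1. Start Month 13 at Study Day 375.
2. Define Baseline as the last pre-infusion value, including a pre-dose Day 1 value, as in section 6.2.1, and limit all post-dose windows to post-infusion assessments.
3. For the assessments that Table 1 schedules weekly (CHOP-INTEND and pulmonary exam), add Day 7, 14 and 21 rows and start Month 1 after the Day 21 visit window, which ends on Day 21 + 2 = 23. Month 1 then runs, for example, from Day 24 to Day 44. A start on Day 15, as the table's own pattern implies, would not be enough because Day 21 would stay inside.
4. Leave the Month 1 window wide for Bayley and milestones. Bayley has no weekly visits, so a narrower window could only lose data.

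The cost is a few lines of SAP text and programming. The downside is that a child with no CHOP-INTEND total from Day 24 to Day 44 has a missing Month 1 value.
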